Other than a phone call from study staff one week post last study drug dose, the study does not have a follow up phase. The purpose of phone call is to follow-up on any symptoms participants may have to the study drug. Since the study drug does not affect alcohol consumption and is only provided at single doses, and since this study does not recruit subjects meeting criteria for DSM-IV alcohol dependence, careful monitoring post-last dose for adverse effects using EKG and biochemistry is sufficient as a safety monitoring plan for this drug.

The DSM plan must indicate that all adverse events during follow-up will be reported (SAEs within 48 hours) to the IRB and NIAAA.

This study does not have a follow up phase, other than a phone call one week after the last study dose. All participants have access to a 24 hour, 7 days/week line to the Principal investigator if participants experience any adverse symptoms.

The DSM plan must briefly describe the procedures for data quality assurance and confidentiality.

Confidentiality risks will be minimized by using randomly coded records and storing signed consent forms and other identifiable information in a locked file cabinet. We will maintain confidentiality by using procedures that are fully-HIPAA compliant and approved by HH and Yale Research Administrations. All information and data concerning volunteers are confidential and never released to anyone outside of the project without the volunteer's written authorization. The identity of participants is never revealed in research reports or conferences. A Certificate of Confidentiality will be obtained.

Protection of these data will be maintained through password protected databases and computer workstations, as well as with auto-locking room doors and locked file cabinets that contain this data. Overview by [name] and audits by Hartford Hospital, Yale University HIC, and NIAAA will ensure proper compliance with these and all confidentiality protocols.

Data quality is assured by careful training of staff members, use of forms designed to minimize errors and oversight from the data management component of the clinical core.

Data will be analyzed and made available to other qualified researchers on request. All data are kept in locked file cabinets in a locked office and all information entered into a database is password protected. Data are kept on average for 5 years following the completion of data analysis.

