AZOD530's blockade will act to “reset” dopaminergic imbalance in extended reward system circuitry of FHP so that abnormal NAcc, ACC, and DLPFC activation during response inhibition will be normalized and more closely resemble that of matched FHN individuals in the placebo condition.

Importance: tests hypothesis of DA/NMDA imbalance in response inhibition circuitry as a risk factor for alcoholism. Logical extension of data gathered in prior phase of CTNA.

Extended network analysis using functional connectivity approaches will show interrelationships among neural circuits responsible for response inhibition (GNG) and motivation (MID) and additionally their alteration by Saracatinib in FHP (exploratory).

3. AZ0D530 trial with fMRI Alcohol Cue Reactivity (ACR) task (AKA ‘NAC’ task). The ACR task in alcohol users is related to the brain's response in reward-related regions to wanting and craving of alcohol versus matched soft drink stimuli. Prior data also suggest that Saracatinib will suppress cue-induced alcohol craving, perhaps more markedly in FHP. **Aim:** to examine NAcc response to alcohol-related versus control images using an existing ACR task.

Major hypothesis. FHP who use alcohol will respond with greater NAcc BOLD signal to alcohol-related cues vs. non-alcohol cues than matched FHN who use alcohol. **Subsidiary hypothesis.** Alcohol-using subjects in general will show a reduced response to alcohol images in the ACR task during the Saracatinib condition, but more markedly in FHP.

Importance: examines additional forms of responsiveness likely relevant to initiation into alcohol misuse.

4. Pilot Task: Pavlovian-to-Instrumental Transfer (PIT) Elaboration of MIDT

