Statistical Parametric Mapping (SPM5) analyses will test pre- to post-treatment differences in fMRI regions of interest (ROIs) during decision making for owned and control items on the symptom provocation task. The primary ROIs for treatment effects include bilateral NAcc, ACC and bilateral OFC. These and other task-relevant ROIs will be defined as 16 mm diameter spheres around x, y, z coordinates determined from our current data. Mean estimates of signal change (i.e., beta-weights from fMRI regression models) within each ROI will be examined separately using Bonferroni correction will be used to guard against alpha inflation due to multiple comparisons. As a secondary analysis, in the event that our new dataset shows somewhat different main effects of task (i.e., peak activation foci in slightly different regions), we can use the Wake Forest University toolbox to draw anatomically-based regions-of-interest. SPM analyses can then test these using averaged % BOLD signal change estimates from the entire region, or SPM small-volume correction to determine the peak group effect difference within the study ROIs.

Mapping Abnormal Responses Across fMRI tasks onto Functional Brain Systems

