The primary outcome for this Aim will be BOLD activation during the A1 phase of the MID task. The effects of Saracatinib treatment on activation will be assessed using linear mixed models. In these models, BOLD response will represent the dependent measure and family history status (FHP vs. FHN) will represent a between-subjects explanatory variable, while treatment (placebo vs. Saracatinib) and ROI (NAcc vs. OFC) will be included as within-subjects factors. All 2-way interactions will be modeled and interpreted using graphical displays and appropriate post-hoc tests. In the above analysis, we anticipate a family history by treatment by ROI interaction explained by significant NAcc decreases and significant OFC increases in BOLD response due to Saracatinib treatment among FHP subjects. Secondary analyses will include the above analysis performed for activation levels observed during the A2 phase and examination of additional ROIs as well as dose and. Similar models as described, excluding phase as a factor, will be used to model BART and EDT outcomes (subsidiary hypothesis). In these models, we expect a family history by treatment interaction such that each of these impulsivity measures are reduced by Saracatinib treatment among FHP individuals.

Aim 2

BOLD signal activation in the anterior cingulate cortex (ACC) observed during False Alarms of the GNG task will represent the primary outcome in this Aim. The effects of Saracatinib treatment on activation will be assessed using linear mixed models with family history (FHP vs. FHN) included as a between-subjects factor and treatment (placebo vs. Saracatinib) and response type (false alarms vs. correct rejections) as within-subjects factors. A significant family history by treatment by response type interaction explained by increased BOLD activation due to Saracatinib during false alarms in both groups, but more markedly in FHN, will be supportive of our hypothesis. We will consider other regions (BA9, BA44/45, BA47, Insula, VS) represented as additional within-subjects factors in the model described above. In this analysis, we expect Saracatinib to reduce BOLD signal activation among FHP in each of the regions during correct rejections.

Aim 3

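### The Bonferroni correction in section 6a has no defined family or alpha and is not carried into the per-region follow-up tests of section 6b; Holm within a closed region family per aim would close the gap

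*Combined protocol and SAP*

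**What the plan says.** Section 6a (General Task Analysis Approaches) extracts a mean signal estimate per region of interest (ROI) and says that these estimates "within each ROI will be examined separately using Bonferroni correction will be used to guard against alpha inflation due to multiple comparisons". On which regions count, it says "The primary ROIs for treatment effects include bilateral NAcc, ACC and bilateral OFC" and continues "These and other task-relevant ROIs will be defined as 16 mm diameter spheres". It states neither an alpha nor a number of tests. The same paragraph sets the comparison "during decision making for owned and control items on the symptom provocation task", which is not among the tasks in sections 4 and 5.

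Section 6b (Analyses Based on Specific Aims) uses linear mixed models. For Aim 1, "treatment (placebo vs. Saracatinib) and ROI (NAcc vs. OFC) will be included as within-subjects factors", and interactions are to be "interpreted using graphical displays and appropriate post-hoc tests". The expected pattern is a three-way interaction explained by a significant NAcc fall and a significant OFC rise in family-history-positive (FHP) subjects. Aim 4 reuses this model with cue type added. Aim 2 takes ACC as its primary outcome and then says "We will consider other regions (BA9, BA44/45, BA47, Insula, VS) represented as additional within-subjects factors", expecting a drug-related reduction in FHP subjects in each of them during correct rejections. Aim 3 uses NAcc alone. Section 6b mentions no multiplicity adjustment.

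Hypothesis 2 in section 4 names a further set for the Go/No-Go task: "abnormal NAcc, ACC, and DLPFC activation during response inhibition will be normalized".

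**The concern.** The plan says that it controls alpha inflation over regions, but a reader cannot work out the divisor from 6a or tell whether the correction governs the tests in 6b. Those tests include per-region contrasts, the kind of test that 6a says it corrects. If alpha is 0.05, a NAcc follow-up p-value of 0.03 counts as significant if it is left unadjusted, and as non-significant if Bonferroni is applied over even two regions. Nothing in the plan fixes that choice before the data are seen. Section 6b treats significance as support for the hypotheses, so the choice affects what is concluded.

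**Working it through.** **No figure to reproduce.** The documents give no alpha, sidedness, effect size or number of tests. Two-sided alpha 0.05 is assumed throughout. The sample size (45 FHP and 45 family-history-negative) is from section 5.2.

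**1. Region sets side by side.**

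| Place | Regions | How ROI is handled |
|---|---|---|
| 6a | NAcc, ACC, OFC, and others | separate tests, Bonferroni |
| 6b Aims 1 and 4 | NAcc, OFC | two-level factor, then follow-up tests |
| 6b Aim 2, primary | ACC | no ROI factor |
| 6b Aim 2, added | BA9, BA44/45, BA47, insula, VS (ventral striatum) | additional within-subject factors |
| 6b Aim 3 | NAcc | no ROI factor |

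A family history by treatment by ROI interaction is one test and needs no divisor. Multiplicity arises when the effect is then tested in each region, or when Aim 2's five added regions are read one by one.

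**2. Thresholds for one NAcc follow-up contrast,** alpha/m:
- unadjusted: 0.05
- m = 2 (NAcc, OFC): 0.05/2 = 0.025
- m = 3 (6a list, sides pooled): 0.05/3 = 0.0167
- m = 5 (6a list, left and right NAcc and OFC counted separately): 0.05/5 = 0.01

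**3. Familywise error if the follow-up tests are left unadjusted.** For independent tests it is 1 − 0.95^m. Regions in the same subjects are correlated, so simulated values at correlation 0.8 are shown as well.

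| m | independent | correlation 0.8 |
|---|---|---|
| 2 | 9.8% | 7.8% |
| 3 | 14.3% | 9.9% |
| 5 | 22.6% | 12.7% |

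**4. What the choice of threshold does to power.** For a paired drug-placebo contrast in 45 FHP subjects, the normal approximation is Φ(dz√45 − z), where dz is the standardised paired effect and z the two-sided critical value. Take dz = 0.418, so dz√45 = 2.80.
- at 0.05: Φ(2.80 − 1.96) = 80%
- at 0.025: Φ(2.80 − 2.24) = 71%
- at 0.0167: Φ(2.80 − 2.39) = 66%
- at 0.01: Φ(2.80 − 2.58) = 59%

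**5. Holm against Bonferroni.** Holm compares the smallest p-value with alpha/m, the next with alpha/(m − 1), and so on, stopping at the first failure. Every cut-off is at least alpha/m, so each Bonferroni rejection is also a Holm rejection, and familywise error stays at or below alpha. Simulated average power per truly active region, with n = 45, assumed dz = 0.4, correlation 0.45 and paired t tests:

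| Regions tested | Truly active | Bonferroni | Holm |
|---|---|---|---|
| 2 | 2 | 64% | 70% |
| 5 | 5 | 50% | 60% |
| 5 | 2 | 50% | 52% |
| 5 | 1 | 50% | 50% |

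The Bonferroni figures agree with the noncentral t distribution (noncentrality 0.4 × √45 = 2.68, 44 degrees of freedom): 64.2% at 0.025 and 50.3% at 0.01. Simulation runs differ by about one percentage point.

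**The case against.** The Bonferroni sentence stands under the general approach and nothing in 6b cancels it, so the follow-up tests of Aim 1 can be read as covered by it. Section 6a also anticipates lists that vary by task. This is fair: the correction is stated but undefined and unlinked. A reader might infer that the plan has no guard against alpha inflation at all; the text does not support that. The objection does not settle which regions count, and the mention of a task from outside this trial makes it doubtful that the paragraph was written for these analyses.

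A reader might also infer that every 6b model needs a divisor for regions. It does not: the interactions are single tests, and neither Aim 3 nor Aim 2's primary model has an ROI factor. The 6a per-region test and the 6b interaction also estimate different things, so the threshold conflict concerns the follow-up contrasts only.

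If Aim 1 were claimed only when both the NAcc and the OFC contrast are significant, no adjustment would be needed. The plan states no such joint rule.

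The study is a pilot meant to estimate effect sizes, which limits the consequence. It does not remove it, because 6b calls a significant interaction supportive and expects significant changes in individual regions.

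Bonferroni is itself valid, and Holm's gain depends on how many regions are active. Both points stand. The argument for Holm is that it costs no error control and cannot lose power.

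**Conclusion.** The point holds for the per-region follow-up contrasts of Aims 1 and 4 and for Aim 2's five added regions. The correction in 6a has no stated alpha and no closed family, sits in a paragraph about another task, and is not linked to 6b. At an assumed alpha of 0.05 the threshold for one NAcc follow-up contrast ranges from 0.05 to 0.01, which moves a contrast with 80% power down to 59%. Replacing Bonferroni with Holm gains about 6 percentage points of average power with two active regions and about 10 with five, under the assumed effect of 0.4 and correlation 0.45, and almost nothing if one region is active.

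A reader might go further and pool all aims, the BART and EDT outcomes and Aim 2's added regions into one large familywise error. The documents do not support that count: BART and EDT are labelled subsidiary, the added regions enter a model as factors, and outcomes from the same subjects are not independent. Nor is adjustment across the four aims required. Each aim has its own stated hypothesis, Aim 4 is labelled a pilot task, and whether to adjust across them is a trade-off for the investigators.

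**What to change.** 1. Rewrite the 6a ROI paragraph for this trial's tasks and its placebo-saracatinib comparison, and state alpha and sidedness.
2. Replace Bonferroni with Holm, and say that it applies to the per-region follow-up tests in 6b and not to the single interaction tests.
3. Close the family for each aim: NAcc and OFC for Aims 1 and 4; ACC as the single primary region for Aim 2, with its five added regions as a secondary Holm family. State whether left and right are averaged or counted as separate tests, and reconcile the regions in Hypothesis 2 with this list.
4. Label all other regions exploratory, with estimates and confidence intervals.

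This costs only wording: no added subjects, visits or scans. There are two downsides. Some follow-up results that would be significant unadjusted will no longer be so. Simultaneous confidence intervals that match Holm are also less simple than Bonferroni intervals.

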A Phase One Study Investigating the Tolerability and Effects of AZD0530 on Functional Neuroimaging Response in Individuals With or Without a Family History of Alcoholism

NCT02262026

12/17/18

“Functional Neuroimaging of Alcoholism Vulnerability: Glutamate, Reward, Impulsivity, and Pavlovian-to-Instrumental Transfer (PIT), Part II - Saracatinib”

1. Introduction:

The purpose of this pilot study is to evaluate the role of Saracatinib in clarifying the neurobiology of alcoholism risk. This is a 1-site, randomized, within subjects, counterbalanced double-blind study of one dose (125 mg) of Saracatinib and placebo. This project explores the effects of 1 dose of Saracatinib (an experimental Fyn-Src family protein tyrosine kinase inhibitor drug (AZD0530)), in a double-blind, randomized, counterbalanced manner on alcoholism risk-relevant tasks. Drug/placebo will be administered on 2 separate visits separated by 1 week following an initial screening visit. More specifically, this project examines 4 functional MRI tasks related to different aspects of reward and/or impulsivity-related behavior in different contexts, compares the underlying neural circuitry across tasks, and uses a pharmacologic probe of the glutamatergic system to examine N-methyl-D-Aspartate and Dopamine (NMDA/DA) interactions. The combined measures provide the opportunity to advance our understanding of specific aspects of brain function related to familial alcoholism vulnerability in an already well-characterized population as some members evolve into alcohol abuse. In addition, as well as conventional within-task analyses, functional network connectivity and allied approaches will be used to examine brain networks across the above tasks.

2. Background:

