Subjects may find the battery of psychiatric and psychological tests tedious and boring, or intrusive. If the former is the case, additional brief breaks will be given during assessment. The latter concern is addressed through use of trained interviewers who have experience discussing sensitive material with clinical research subjects. However, if a subject finds a topic too uncomfortable, those questions will be skipped, or with severe reactions, subjects will be reminded they can discontinue participation without penalty.

Following study completion, subjects will only be allowed to be discharged when they have minimal subjective reports of intoxication or sedation, their vital signs have returned to baseline, and they have been assessed by either an RN or physician.

MRI:

The FDA has approved the MRI system and the scanning protocols to be used. The MRI scanning procedure in a 3 Tesla system is safe in normal healthy humans. However, subjects who could suffer potential risks from the MRI scanning procedure include those with metal implants (pacemaker, metal rods, bone screws, orthodontics, metal flakes from metalworking). Subjects are told during the informed consent process about the need to carefully screen for metal implants or any other exposure to metal in the body. Subjects who could potentially suffer harm will be screened for metal prior to scanning using a HH Radiology Department screening checklist. Although there is no proven harm to developing fetuses, women will be screened for pregnancy before scanning. Subjects with claustrophobia may experience some anxiety symptoms, and will be discouraged from participating. Subjects who feel claustrophobic during the experiment will be encouraged to notify experimenters at any time to discontinue scanning. There are no known risks associated with the visual or auditory stimuli presented during recording of event-related fMRI.

Structural MRI: Performed on day 1 only.

Functional MRI tasks: (both study days)

The Monetary Incentive Delay (MID) Task:

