Linear mixed models will be used to evaluate the effects of family history on NAcc BOLD response during the ACR task. These models will include family history (FHP vs. FHN) as a between-subjects factor and type of Cue (ETOH-related vs. non-EOTH) as a within-subjects factor. We anticipate a significant group by cue interaction such that FHP subjects will respond with greater NAcc BOLD signal to alcohol-related cues vs. non-alcohol cues compared to matched FHN subjects and subsequently experience a greater reduction in NAcc BOLD response following Saracatinib administration.

Aim 4

The same statistical models described for Aim 1 will be used to evaluate the effects of Saracatinib and family history on NAcc and OFC activation during the A1 phase of the PIT-in

modified MID task. In these models, however, we will include Cue Type (PIT-related vs. Non-PIT-related) as an additional within-subjects variable. We expect a significant family history by treatment by cue type by region interaction explained by significant NAcc decreases and significant OFC increases in BOLD response due to Saracatinib treatment among FHP subjects, with these effects most exaggerated during the presentation of PIT-related cues. In addition, using regression we can test whether PIT responses (using the out-of-scanner version used in all data from study 126237) show the expected learning effect.

7. Risks and Data Monitoring Plan:

Under some circumstances, it can be a risk for genetic information about subjects to be known. Variation in some genes is known to be directly related to risk for certain illnesses. Other genes we will be studying in subject DNA may be shown at some point in the future to be related to illnesses. Since the results of these genetic tests may allow prediction of risk of illness in some cases, we will make every effort to keep the results confidential (only scientists working on this research project will know the results). We will not make any of our laboratory results available to subjects, nor will we add them to any medical record or release them to others.

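### The drug–placebo models in Section 6b have no visit term, so any change between the two visits stays in the error of the family history × treatment comparisons

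*Combined protocol and SAP*

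**What the plan says.** Section 1 describes a randomised, counterbalanced, within-subject comparison: "Drug/placebo will be administered on 2 separate visits separated by 1 week". Section 5.4 has the fMRI tasks run on both study days, and BART and EDT done two hours after dosing.

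Section 6b lists the factors of each linear mixed model:

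- **Aim 1.** Family history between subjects; "treatment (placebo vs. Saracatinib) and ROI (NAcc vs. OFC) will be included as within-subjects factors". The plan adds: "All 2-way interactions will be modeled and interpreted using graphical displays and appropriate post-hoc tests". It anticipates a family history × treatment × ROI interaction, explained by drug effects in each region among FHP subjects.
- **BART and EDT (subsidiary hypothesis).** Similar models, in which "we expect a family history by treatment interaction such that each of these impulsivity measures are reduced by Saracatinib treatment".
- **Aim 2.** Family history, with "treatment (placebo vs. Saracatinib) and response type (false alarms vs. correct rejections) as within-subjects factors"; the anticipated effect is the three-way interaction.
- **Aim 4.** The Aim 1 model, in which "we will include Cue Type (PIT-related vs. Non-PIT-related) as an additional within-subjects variable"; the anticipated effect is the four-way interaction.

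None of these lists visit, period, order or sequence, and Sections 5.1 and 6a supply none. The phase mentioned for BART/EDT is the MID task phase, not a study period. Section 6b does not state the random effects. Aim 3 has no treatment factor and the probabilistic selection task has no model in 6b, so neither is covered here.

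**The concern.** In a two-visit crossover, balancing drug order removes visit bias from the average drug effect. It does not remove the visit shift from each subject's drug-minus-placebo difference. That difference is pushed up in subjects who take drug second and down in those who take it first. If the model has no visit term, this spread is counted as noise.

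A visit shift is plausible. PIT cues are trained, and Section 5.4 places BART and EDT on dosing days while Go/No-Go, IAT and AAT are done at screening. The shift for Go/No-Go may therefore be small.

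Precision is what this pilot is meant to deliver. Section 5.1 gives its purpose as assessing effect size, and Section 6 says the estimates will be used to power later studies. A removable component in the SD widens the reported intervals and shrinks any standardised effect. Separately, no section says that drug order is balanced within FHP and within FHN.

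**Working it through.** **Inputs.** From the documents: 45 FHP and 45 FHN (Section 5.2), two drug visits (Section 1) and the factor lists in 6b. The plan gives no alpha, SD, effect size, power or visit effect, so it has no figure to reproduce. Assumed: two-sided alpha 0.05; SD of the within-subject drug-minus-placebo difference = 1; visit shift π (visit 2 minus visit 1) from 0 to 0.8 of that SD.

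**One value per visit (BART/EDT, or a single region).** Write D = τ + sπ + e, where τ is the group's drug effect, s = +1 if drug comes second and −1 if first, and SD(e) = 1. Without a visit term the residual variance is 1 + π²; with it, 1. For the difference between groups, SE = √(2/45) × √(1 + π²) = 0.211 × √(1 + π²). Power is from the noncentral t with 88 df.

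| π | SE ratio | SE | 95% half-width | Power, 0.4 SD | Power, 0.6 SD | Power, 0.8 SD |
|---|---|---|---|---|---|---|
| 0 | 1.00 | 0.211 | 0.42 | 47% | 80% | 96% |
| 0.2 | 1.02 | 0.215 | 0.43 | 45% | 79% | 96% |
| 0.3 | 1.04 | 0.220 | 0.44 | 44% | 77% | 95% |
| 0.5 | 1.12 | 0.236 | 0.47 | 39% | 71% | 92% |
| 0.8 | 1.28 | 0.270 | 0.54 | 31% | 59% | 83% |

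With visit in the model, simulated power for 0.6 SD stays at about 80% at every π.

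**Role of the order split (simulation).**

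- *Balanced overall only:* type I error without visit is 4.8–5.2%. The realised split moves the estimate by 2π(p_FHP − p_FHN), where p is the proportion taking drug second. With 45 of 90 in each order, this shift has SD 0.21π and averages zero over randomisation.
- *Same split in both groups:* the unadjusted test is conservative. At π = 0.5 the reported SE is 0.2355 against a true 0.211, type I error is 2.9% and power for 0.6 SD is 73%. At π = 0.8 these last two are 1.2% and 62%.

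**Two regions in one model.** Let ρ be the correlation between the two regional differences (assumed 0.3–0.7) and V the subject-by-region variance (assumed 0–1). The SE ratios are:

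- *Family history × treatment averaged over regions, subject-by-treatment variation modelled:* √(1 + π²/((1+ρ)/2)). At π = 0.5, ρ = 0.3 this is √(1 + 0.25/0.65) = 1.18; at ρ = 0.7, √(1 + 0.25/0.85) = 1.14. The rise is 2–3%, 5–7%, 14–18% and 32–41% at π = 0.2, 0.3, 0.5 and 0.8.
- *Random intercept only:* √(1 + π²/(1 + (1−ρ)/2 + V)), giving 1–2%, 2–4%, 5–10% and 13–25% at the same π. The three-way SE rises by the same amount, because the residual is pooled.
- *Three-way interaction, subject-by-treatment variation modelled:* √(1 + ((π₁−π₂)/2)²/((1−ρ)/2)). The rise is 0% if the shift is equal in both regions, 2–5% for 0.5 against 0.25, and 9–19% for 0.5 against 0.

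**Effect on a later study.** Suppose a later study uses the same contrast and does model visit, but is planned from the unadjusted SD. Numbers per group for 80% power (exact t) at π = 0.3, 0.5 and 0.8 are:

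- true effect 0.4: 108, 124, 162 instead of 100
- true effect 0.6: 49, 56, 73 instead of 45
- true effect 0.8: 28, 32, 42 instead of 26

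**The case against.** The documents show no visit effect. A training step, a timetable entry or a structural scan on the first day does not prove one, and at π = 0.2–0.3 the loss is only 2–4% of the SE. That stands: the size is conditional, and only a range can be given.

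The anticipated effects in Aims 1, 2 and 4 are higher-order interactions, from which a common visit effect cancels. That also stands for the estimates. Those tests are touched only if the shift differs by region, response type or cue type, or if the model has a random intercept alone. But family history × treatment is the stated test for BART/EDT, albeit a subsidiary hypothesis. Aim 1, reused for Aim 4, interprets all two-way terms and explains its three-way interaction by single-region drug effects. Aim 2 has no such sentence on two-way terms, so the point is weakest there.

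Section 6b is also an outline, and a visit term would be compatible with it. True, but it names its factors one by one, and an analyst who follows the list will leave visit out.

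Finally, the harm is conservative: no bias over randomisation, no inflated type I error, and no power target to miss. All correct. Lost precision still matters in a study whose output is an effect size and its SD.

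**Conclusion.** The concern holds. The omission is plain in the listed models, and its effect on family history × treatment follows algebraically from the two-visit design. Its size rests on an unknown visit shift: nothing at π = 0, 4% on the SE at 0.3, 12% at 0.5 and 28% at 0.8 for contrasts with one value per visit. In the two-region models the size also depends on the unstated random effects and on the assumed correlation. The harm is lost precision, and it can be removed at analysis. This should be changed, but it does not threaten the validity of the tests. The figures assume two drug visits and would not apply to three.

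**What to change.** - Add visit as a fixed within-subject factor to the Aim 1, Aim 2, Aim 4 and BART/EDT models, and to any other model that uses both drug visits.
- Where a higher-order interaction is the anticipated test, also add visit × ROI, visit × response type or visit × cue type.
- State the random effects, in particular whether subject-by-treatment variation is modelled.
- Use family history × visit as a sensitivity analysis.
- Report the drug-order split within FHP and FHN, and balance order within group for subjects not yet randomised.
- Reconcile the passages that define the visit factor. Sections 1 and 2a give two drug visits. Section 3 gives both two study days and three experimental visits. The out-of-scanner task heading gives three experimental days, and the timeline note gives four appointments. Section 7 lists two active doses or placebo.

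The cost is SAP wording and about one or two degrees of freedom per model, with no new data. If there is no visit effect, the SE is 0.212 with visit against 0.210–0.211 without when order is not balanced within group, and identical when it is.
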